Joslin Diabetes Center

Committee on Human Studies

Application for Review and Approval of Research and Training Projects Involving Human Research

Principal Investigator: [name].

Co-Investigator(s): [name]., M.P.H., [name] MEd, LDN, RD, C.D.E., [name], R.N., B.S.N., C.D.E., [name]., [name]., [name], MEd, RCEP, C.D.E., [name] B.Sc., [name], B.A.

Project Title: Barriers to Adherence to Recommended Follow-up in Women with a History of Gestational Diabetes

Funding: Roche Diagnostics

Study Contact: [name] [contact]

1. PURPOSE OF PROTOCOL:

To conduct an intervention study to improve adherence rates to post partum screening and attainment of weight loss targets in women with gestational diabetes through a pilot randomized controlled trial, involving the following three groups:

Group 1: (see Table 1) Standard care—Per usual care patients will receive a letter reminding them to schedule a 75 gram 2 hour Oral Glucose Tolerance Test (OGTT) 6 weeks post partum and see their Joslin provider to discuss the results. At 12 months +/- 3 months, we will ask women if they received a 75 gram 2 hour OGTT or had a fasting glucose lab test. For those women who have received this test, we will request the results as well as a documented weight from the study participant via self-report or from the participant's health care provider. In addition, participants will be asked to complete a questionnaire at 6 weeks to 3 months, 6, 9, and 12 months postpartum.

Group 2: (see Table 2) On-line nutrition and physical activity class—In addition to standard care described above, study subjects will participate in 1.5 to 2 hours nutrition and physical activity online class at 6 weeks to 3 months and 9 months. The online classes will be hosted via a highly secure online platform- Brainshark. Women will also be asked to self-report their weight at these times. At 12

Approved by
JDC/ CHS
CHS#2012-16

A handwritten signature in blue ink, appearing to read 'JDC'.

Date: 03/10/2014

months +/- 3 months, we will ask those women who chose to receive diabetes screening (either a 75 gram 2 hour

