Informed Consent	75 gram 2-hour OGTT (at Joslin or through OB)	Completion of Study questionnaires	Completion of Study questionnaires	Completion of Study questionnaires	Completion of Study questionnaires
Determination of Eligibility	Visit to Joslin provider				Results of 75 gram 2-hour OGTT or glucose (if done) Obtain weight
Randomization					

Table 2 - Group 2 Standard Care with Group Nutrition Visits

Contact 1 (Enrollment/ Randomization)	Contact 2 (6 weeks post-partum)	Contact 3 (6 weeks to 3 months post-partum)	Contact 4 (6 months post-partum)	Contact 5 (9 months post-partum)	Contact 6 (12 months post-partum)
Informed Consent	75 gram 2-hour OGTT (at Joslin or through OB)	Completion of Study questionnaires	Completion of Study questionnaires	Completion of Study questionnaires	Completion of Study questionnaires
Determination of Eligibility	Visit to Joslin provider	Participate in Nutrition and physical activity Class online Record weight		Participate in Nutrition and physical activity Class online Record weight	Results of 75 gram 2-hour OGTT or glucose (if done) Obtain weight
Randomization					

Table 3 - Group 3 Standard Care with Nutrition Group Visits and block Blood Glucose Checking

Visit 1 (Enrollment/ Randomization)	Visit 2 (6 weeks post- partum)	Visit 3 (6 weeks to 3 months post- partum)	Visit 4 (6 months post- partum)	Visit 5 (9 months post- partum)	Visit 6 (12 months post- partum)
Informed Consent	75 gram 2-hour OGTT (at Joslin or through OB)	Completion of Study questionnaires	Completion of Study questionnaires	Completion of Study questionnaires	Completion of Study questionnaires
Determination of Eligibility	Visit to Joslin provider	Participate in Nutrition and physical activity Class online		Participate in Nutrition and physical activity Class	Results of 75 gram 2-hour OGTT or glucose (if done)

Approved by

JDC/ CHS

CHS#2012-16

AK

		Record weight		online Record weight	Obtainweight
		Monthly BG checking with BG meter, 4 times a day for 4 consecutive days	Monthly BG checking with BG meter, 4 times a day for 4 consecutive days	Monthly BG checking with BG meter, 4 times a day for 4 consecutive days	
Randomization					

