3. INCLUSION / EXCLUSION CRITERIA

Inclusion criteria:

1. Gestational Diabetes
2. Age between 21 and 45 years
3. Preconception BMI 19-40
4. Seen for at least 2 visits in the Diabetes in Pregnancy Program during their pregnancy
5. Singleton pregnancy

Exclusion criteria

1. Preexisting diabetes or diabetes diagnosed at the 6 week 75 gram 2 hour OGTT

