4. DATA ANALYSIS / SUBJECT SELECTION

For aim 1, we will calculate the proportion of women who received postpartum diabetes screening in each group using intention-to-treat analysis. We will calculate the association between the interventions versus standard care by calculating chi-square and p-values to assess statistical significance. For aim 2, we will evaluate the association between our intervention and continuous blood glucose levels among women who received the 12-month 75 gram 2 hour OGTT or glucose. We will use ANOVA to calculate F-statistics and p-values to determine whether the intervention was associated with improved blood glucose levels compared to the standard care. Similarly, for aim 3, we will evaluate the association between our intervention and continuous weight measurements using ANOVA. As a secondary hypothesis, we will use multivariable binomial regression to evaluate the association between age, race/ethnicity, sociodemographic factors, self-care, perceived infant care giving needs, fear of diabetes, and access/satisfaction with medical care, and adherence to postpartum diabetes screening at 12 months. We will calculate risk ratios and 95% confidence intervals, adjusting for potential confounders, including sociodemographic factors. We will primarily assess these results for directionality. We will use SAS version 9.2 (Cary, NC) for all analyses.

The proposed project is a pilot study. Therefore, we anticipate having limited power to detect statistically significant results. However, the direction and magnitude of the associations will provide necessary data required for a larger research study to further improve adherence to diabetes screening guidelines after GDM, as well as potentially improve blood glucose results for women in the first year postpartum and reduce weight retention. As such, this study is clinically significant, given that it may provide insight into how to improve adherence to follow-up diabetes screening and subsequent prevention or delayed diabetes diagnosis. This data analysis will be performed by [name] and [name].

Local Interim Data Analysis/Data Monitoring Plan

Approved by

JDC/ CHS

CHS#2012-16

AP

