The data for each subject will be extracted from her medical record data in Joslin Diabetes Center for statistical analysis by [name]. After abstracting the data, it will be merged via the key with the personal identifiers dataset housed on [name] computer (PI) with questionnaire data by [name] and the Research Assistant. Once this merge takes place, personal identifiers will be removed and only the unique study ID will remain attached to this information. As described in Section 6, the key to the code, linking the subject's personal information to the subject will be kept in a locked file in Joslin Diabetes Center. Only [name] (PI) and [name] RD will have access to the key to the code.

Only the following data from medical records will be sent to the co-investigators for data analysis:

- Height
- Weight immediately before pregnancy
- Weight prior to delivery
- Age at delivery
- Gestational age at delivery
- Race/ethnicity
- Marital status
- Education level
- Family income
- Use of insulin in pregnancy
- Contraceptive use/type
- Gravidity and parity
- Breast feeding exclusively (yes or no)
- Bottle feeding exclusively (yes or no)
- Mixed breast and formula – how many bottles of formula/day
- Breast feeding exclusively duration
- Mixed breast and bottle duration
- Weight at 3 months and 9 months (groups 2 and 3) and 1 year +/- 3 months (all 3 groups)
- 6 week glucose tolerance test results
- 1 year glucose tolerance test results
- Barriers to adherence—healthy eating and physical activity (from questionnaire)
- Partner support
- self-care and –efficacy,
- perception of infant care giving needs,
- knowledge and fear of diabetes diagnosis,
- depressive symptoms (Edinburgh Postpartum Depressive Scale)
- satisfaction with medical care
- self-report of physician referral for postpartum diabetes screening
- History of other pregnancy complications

The co-investigators will not receive the PHI-containing dataset.

Please answer the following questions:

- Will medical history/clinical information be obtained from the subjects' medical records for the purpose of this study? If yes, please list what information will be recorded.

Approved by
JDC/ CHS
CHS#2012-16

YES

- Height
- Weight immediately before pregnancy
- Weight prior to delivery
- Age at delivery
- Gestational age at delivery
- Race/ethnicity
- Use of insulin in pregnancy
- Contraceptive use/type
- Gravidity and parity

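### Aim 2 tests 12-month glucose by unadjusted ANOVA in women who chose testing, and leaves out the 6-week OGTT that could sharpen the comparison and check the groups

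*Combined protocol and SAP*

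**What the plan says.** Section 4 of the combined protocol and SAP defines the Aim 2 outcome as "continuous blood glucose levels among women who received the 12-month 75 gram 2 hour OGTT or glucose". The method is one sentence: "We will use ANOVA to calculate F-statistics and p-values", in order to "determine whether the intervention was associated with improved blood glucose levels compared to the standard care". No baseline value, covariate or change score is named. Adjustment for confounders is mentioned only for the secondary regression on screening adherence.

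The 6-week test appears in four other places:

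- Tables 1 to 3 (Section 2) place a "75 gram 2-hour OGTT (at Joslin or through OB") at the 6-week contact in all three groups, one contact ahead of the first class.
- Section 1 shows that it is usual care, prompted by a "letter reminding them to schedule a 75 gram 2 hour Oral Glucose Tolerance Test (OGTT) 6 weeks post partum".
- Section 9 lists "6 week glucose tolerance test results" among the items taken from the medical record and sent to the co-investigators for analysis.
- Section 3 gives its only stated use, the exclusion of women with "diabetes diagnosed at the 6 week 75 gram 2 hour OGTT".

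On timing, Section 1 says that in Groups 2 and 3 "study subjects will participate in 1.5 to 2 hours nutrition and physical activity online class at 6 weeks to 3 months and 9 months". Meter testing in Group 3 runs from month 3 to month 9. Section 2 allows enrolment from the third trimester to 3 months postpartum.

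**The concern.** The plan expects to hold an earlier value of the same biomarker, scheduled before either intervention starts, but gives it no role in the glucose analysis. Two things are lost.

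**Precision.** With at most 10 women per group, any variance that the 6-week value explains is worth having. Section 4 says that the direction and size of the associations are meant to inform a larger study, so the width of the interval matters more than the p-value.

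**A check on comparability.** Aim 2 analyses only women who choose 12-month testing. Aim 1 hypothesises that uptake differs by group. If it does, randomisation no longer guarantees that the analysed groups are alike. Setting out the 6-week values of the women who contribute would be a direct look at this, and the plan has none.

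**Working it through.** The documents give no power calculation, standard deviation or correlation for Aim 2, so there is no stated figure to reproduce.

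**Inputs.** From Section 2: 30 women, 10 per group. Assumed: 7 or 5 per group with a 12-month value; correlation ρ between 6-week and 12-month fasting glucose of 0.3, 0.5 or 0.7; equal spread at the two times; two-sided 5% level. Results are in units of the SD of 12-month glucose.

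**Formulas.** 95% CI half-width for a difference between two of the three groups, n analysed per group:

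- ANOVA of the 12-month value: t(0.975; 3n − 3) × √(2/n).
- ANCOVA on the 6-week value: t(0.975; df) × √[(2/n)(1 − ρ²)(1 + 1/(df − 1))], with df = 3n − 4. The last factor is the expected cost of chance imbalance in the covariate.
- Change score: t(0.975; 3n − 3) × √[(2/n) × 2(1 − ρ)].

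**Worked case, n = 10, ρ = 0.5.** ANOVA: 2.052 × √0.2 = 0.918. ANCOVA: 2.056 × √(0.2 × 0.75 × 1.04) = 0.812. Ratio 0.812/0.918 = 0.88.

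**Half-widths, same women in both models** (ratio to ANOVA in brackets):

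| n per group | ANOVA | ANCOVA, ρ 0.3 | ρ 0.5 | ρ 0.7 |
|---|---|---|---|---|
| 10 | 0.918 | 0.894 (0.97) | 0.812 (0.88) | 0.669 (0.73) |
| 7 | 1.123 | 1.109 (0.99) | 1.007 (0.90) | 0.830 (0.74) |
| 5 | 1.378 | 1.393 (1.01) | 1.264 (0.92) | 1.043 (0.76) |

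**Detectable difference at 80% power, n = 10.** ANOVA 1.30 SD; ANCOVA 1.27, 1.15 and 0.95 SD at the three correlations.

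**Change score, n = 10.** Half-widths 1.086, 0.918 and 0.711. It is worse than the plain ANOVA at ρ = 0.3, equal at 0.5, and worse than ANCOVA throughout.

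**If the 6-week value is missing for some.** Suppose all 10 per group have a 12-month value but only 7 also have a 6-week value. ANCOVA in the 7 has half-width 1.109, 1.007 or 0.830, against 0.918 for ANOVA in all 10. The adjusted interval is then wider at ρ = 0.3 and 0.5, and about 10% narrower at 0.7 (0.830/0.918 = 0.90).

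**The case against.** A reader might infer that, without a baseline, the claim of improvement is unsupported, because a 12-month difference could have been present at 6 weeks. The documents do not support that reading. The sentence in Section 4 ends in a comparison with standard care, and Section 2 speaks of lower glucose values. Neither claims change within a woman. A randomised comparison of follow-up values is valid without a baseline. Chance imbalance at 6 weeks has a standard error of √(2/10) = 0.45 SD at 10 per group and √(2/5) = 0.63 SD at 5, but this is sampling error that the F-test already carries. What threatens validity is self-selection into 12-month testing, and adjusting for one glucose value does not cure it.

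A second tempting inference is that the data are certain to be in hand. The test is usual care and may be done through an obstetrician, whereas Section 9 describes extraction from the Joslin record. The release form in Section 2 is tied to women who report screening, and no separate step retrieves an outside 6-week result. Missing values must be expected.

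Third, the value is not always a clean baseline. Women may be randomised, unblinded, before the 6-week test, so having the test could itself depend on group. Filling in a mean and adding a missing indicator would then condition on something affected by assignment. It may not even pay: a simulation of that model with 5 per group, ρ = 0.4 and 30% missing gave intervals about 5% wider than ANOVA. The class window also opens at 6 weeks, so a late test could follow the first class.

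All of this stands. It limits the remedy, but it does not remove the case for reporting the 6-week values or for a supporting adjusted analysis.

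**Conclusion.** The point holds as a missed opportunity in the Aim 2 analysis, not as an invalid test. The plan schedules the 6-week OGTT in every group and lists it for the analysts, then uses it only for eligibility. It forgoes some precision and leaves no check that the women analysed in each group were alike at 6 weeks.

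The gain in precision rests on an assumed correlation. With complete data at 10 per group the interval narrows by about 3% (ρ = 0.3), 12% (0.5) or 27% (0.7). At 5 per group and ρ = 0.3 it widens by about 1%. With missing 6-week values, an adjusted model in fewer women can be less precise than the ANOVA in all tested women. The comparability check is useful at any correlation. The calculation also assumes that the fasting component of the 6-week OGTT is recorded, which the documents do not spell out. Excluding diabetes at 6 weeks restricts the range of the covariate and may pull the correlation towards the lower end.

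**What to change.** In Section 4, under Aim 2:

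1. Report 6-week fasting glucose by group among the women who contribute a 12-month value, with the number missing in each group.
2. Keep the unadjusted ANOVA in all tested women. Beside it, pre-specify an ANCOVA of 12-month fasting glucose on group plus 6-week fasting glucose, in women with both values and a 6-week test dated before the first class. Group 1 has no class, so state a matching cut-off date for that group.
3. Match fasting with fasting. Do not use a change score, and do not rely on a missing indicator.
4. Report the observed 6-week to 12-month correlation, which the larger study would need.

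**Cost.** No new visit or sample is needed. The analysts need the dates of the 6-week test and first class, and tests done through an obstetrician may need an added retrieval step. The adjusted model spends one degree of freedom and loses women without a 6-week test. For some women the covariate is measured after randomisation, so the adjusted result should be read as supportive.

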OGTT or a fasting glucose lab test) to provide the results of either of these tests, as well as a documented weight. The weight can either be self-reported or from their health care provider at 12 months (+/- 3 months postpartum). Participants will also be asked to complete a questionnaire at 6 weeks to 3 months, and 6, 9, and 12 months postpartum.

Group 3: (see Table 3) On-line nutrition and physical activity class and block blood glucose testing— This group will take part in the above-mentioned standard care and on-line nutrition and physical activity classes at 6 weeks to 3 and 9 months. In addition, participants in this group will take blood glucose levels with provided meters and test strips four times a day for 4 consecutive days once a month starting at 3 months postpartum and concluding at 9 months postpartum to check patterns of glucose before breakfast and 2 hours after each meal. Women will also be asked to self-report their weight at these times. For those women who choose to have diabetes screening at 12 months +/- 3 months through either a 75 gram 2 hour OGTT or a fasting glucose taken at a laboratory, we will request the test results at that time point. We will also collect the study participants weight from either self-report or their health care provider at 12 months postpartum. Each participant will be asked to complete a questionnaire at 6 weeks to 3months, and 6, 9, and 12 months postpartum.

OUTCOMES:

1. Adherence to diabetes screening using the 75 gram 2 hour OGTT or fasting blood glucose at 12 months (+/- 3 months)
2. Lab results from the fasting glucose test or results from a 75 gram 2 hour OGTT at 12 months among women who choose to take the diabetes screening test.
3. Postpartum weight loss (target 7% less than the pre-pregnancy weight for overweight/obese women and back to pre-pregnancy weight for normal BMI women). This will be based on medical record information on pre-pregnancy weight and self-reported or health-care provider reported weight at 12 months.

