4. Determine to what extent barriers to health impact adherence rates to post partum screening and weight loss targets through a web-based questionnaire collected on the 6 weeks to 3 months, 6, 9, and 12 month questionnaires. These questionnaires will assess whether: lack of self care, perception of high infant care giving needs, fear of diabetes diagnosis and postpartum depressive symptoms, difficulty accessing medical care, dissatisfaction with medical care or primary care physician not recommending screening are associated with poorer adherence to diabetes screening guidelines and weight loss goals.

Study aims are:

1. Determine the extent to which women who receive a postpartum group nutrition intervention and/or block blood glucose testing return for a 12 month (+/- 3 months) follow-up screening for diabetes with either a fasting blood glucose test or a 75 gram 2 hour OGTT compared to women who receive standard care. *We hypothesize that women in Group 3 will be the most likely to return for screening at their 12 month follow-up (+/-3 months).*
2. Determine the extent to which women who choose to have diabetes screening conducted at 12 months postpartum and who receive a postpartum group nutrition counseling intervention and/or block blood glucose testing are more likely to have fasting glucose or a 75 gram 2 hour OGTT results within normal range at 12 months (+/- 3months) compared to women who receive standard care.
3. Determine the extent to which women who receive a postpartum on-line nutrition and physical activity counseling intervention and/or block blood glucose testing will meet postpartum weight goals at 12 months postpartum (i.e. more likely to lose 7% of their pre-pregnancy body weight if

Approved by

JDC/ CHS

CHS#2012-16

MM

Date: 03/10/2014

they have a BMI ≥ 25 or return to their pre-pregnancy weight if their BMI < 25) compared to women who receive standard care.

2 STUDY DESIGN:

METHODS:

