Proposed Study Design: This is a pilot study, where we propose to conduct a 3-grouped randomized controlled trial to evaluate whether a 1 ½ to 2 hour on-line nutrition and physical activity intervention +/- block testing of blood glucoses fasting and 2 hours after each meal for 4 days/month from starting at 3 months postpartum and concluding at 9 months postpartum will 1) improve adherence to the receipt of diabetes screening at 12 months postpartum through the recommended 75 gram 2 hour glucose tolerance test or fasting blood glucose test, 2) lower glucose values on the 75 gram 2 hour oral glucose tolerance test or fasting blood glucose test and 3) improve attainment of weight loss targets among women with a recent history of GDM. Patients will participate in an online nutrition and physical activity class at 6 weeks to 3 months and 9 months for women assigned to both groups 2 and 3. For those women assigned to group 3, they will also do block testing using an assigned blood glucose meter and test strips 4 times a day for 4 consecutive days each month, starting at 3 months and ending at 9 months. Women will have the option of submitting meter BG data via e-mailed logs or downloading directly to the clinic using Diasend software. More information about this will be discussed below. Once downloaded, the Diasend software creates a PDF document with all recorded blood glucose values. For purposes of this study, we will obtain a Diasend account specific to this study, which will allow women to download blood glucose information with an anonymous unique identifier that can be accessed by the study's Principal Investigator and CITI-certified, IRB-approved research assistant. Upon accessing the PDF document with the blood glucose meter information, both the PI and the Research Assistant can link blood glucose data with questionnaire and other health information collected in this study through the unique identifiers. More information about the security of the account and linking of data is provided below in Section 6.

On-line Nutrition and Physical Activity Counseling:

The nutrition and physical activity topics for groups 2 and 3, which will be taught using a web-based platform will include the following information by nutrition visit. Diet and exercise interventions will be flexible and sensitive to cultural differences.

6 weeks to 3-month on-line class:

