In addition to data management, adverse event reporting will also be recorded and managed by study staff. While we do not anticipate any adverse events, we will ensure all study participants are aware of potential benefits and risk of participating in the study. If at any time study participants feel that their participation in the study has resulted in injury (for purposes of this study, it could include bruising from finger sticks), we will advise them to contact our CITI-certified, IRB-approved to directly contact the Principal Investigator of the study. We will immediately report any adverse events to the Joslin IRB. If deemed severe enough, we will halt the study.

5. POSSIBLE BENEFITS:

Individuals in groups 2 and 3 may benefit from learning about healthy nutrition, exercise and weight loss targets to prevent type 2 diabetes in the mother and reduce overweight and obesity in the offspring. Individuals in group 3 may also benefit from finger stick glucose monitoring to assess the effect of various types of food on glycemia, which may provide direct feedback about food choices. On the other hand, individuals in group 1 may benefit from better weight management due to reporting on their weight measurements throughout the study time period. Society may benefit from learning whether a simple lifestyle intervention of diet and exercise education +/- periodic blood glucose monitoring results in increased adherence to recommended 12 month (+/- 3 months) follow-up of screening for diabetes with 75 gram 2 hour OGTT or glucose, as well as improve blood glucose results compared to women who receive standard care. In addition, society may benefit from learning whether a nutrition intervention during the immediate postpartum could aid in women losing 7% of their pre-pregnancy body weight if they have a BMI ≥ 25 and return to their pre-pregnancy weight if their BMI < 25 compared to women who receive standard care. If found to be effective, this intervention may provide insight into how to improve adherence to follow-up diabetes screening and subsequently prevent or delay diabetes diagnosis in a high risk group of women who have had a recent GDM-complicated pregnancy.

Approved by

JDC/ CHS

CHS#2012-16

AK

6.POSSIBLE RISKS:

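### Aim 3 asks whether women meet a BMI-specific weight goal, but the only planned analysis is an ANOVA of continuous weight, so goal attainment is never analysed

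*Combined protocol and SAP*

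**What the plan says.** The weight objective is stated as reaching a target in several places.

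- **Section 1, Outcomes, item 3:** "target 7% less than the pre-pregnancy weight for overweight/obese women and back to pre-pregnancy weight for normal BMI women". The same item gives the data source for the baseline: "This will be based on medical record information on pre-pregnancy weight", combined with a self-reported or provider-reported weight at 12 months.
- **Section 1, Study aims, aim 3:** whether women in the intervention groups "will meet postpartum weight goals at 12 months postpartum", with the goal split at BMI 25, compared with standard care.
- **Section 2, Proposed Study Design:** the third objective is to "improve attainment of weight loss targets among women with a recent history of GDM".
- **Section 5, Possible Benefits:** society may learn whether the intervention "could aid in women losing 7% of their pre-pregnancy body weight" (for BMI of at least 25).

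Section 4 gives Aim 3 one sentence: "Similarly, for aim 3, we will evaluate the association between our intervention and continuous weight measurements using ANOVA". For comparison, the same paragraph plans a binary analysis for the first aim: "For aim 1, we will calculate the proportion of women who received postpartum diabetes screening in each group". The only regression in Section 4 has 12-month screening adherence as its outcome.

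**The concern.** The aim is a yes/no result for each woman, judged against her own pre-pregnancy weight and BMI class. The planned analysis compares mean weight. Followed as written, it yields no attainment rate for any arm, although Section 4 says the pilot is there to supply the direction and magnitude of associations for a larger study. A larger trial built on this aim would need those rates.

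The analysis sentence is also ambiguous. On its face it points to weight itself with no baseline term. Outcome 3, however, rests on both pre-pregnancy and 12-month weight, so change may have been intended. If 12-month weight was meant, randomisation keeps the comparison unbiased, but it carries all the between-woman spread in body size allowed by the eligibility rule "Preconception BMI 19-40".

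**Working it through.** **1. Endpoint against analysis.** No arithmetic is needed here. Outcome 3, Aim 3, the design statement and the benefits section all describe reaching a target. In Section 4, proportions and chi-square belong to Aim 1, the binomial regression belongs to screening adherence, and Aim 3 has the ANOVA only. The monitoring plan that follows adds response rates, adherence to the intervention and data checks. Nothing in the available text computes goal attainment.

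**2. Can a comparison of means stand in for attainment?** Constructed example: every woman starts at 80 kg with BMI of at least 25, so the goal is 80 × 0.93 = 74.4 kg or less.

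- Arm A: five women at 74 kg and five at 84 kg. Mean 79 kg, 5/10 attain.
- Arm B: ten women at 79 kg. Mean 79 kg, 0/10 attain.

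The mean weights are equal, and so are the mean changes (−1 kg), yet attainment differs by 50 percentage points. Choosing change instead of weight does not close the gap.

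**3. Precision if 12-month weight is analysed without baseline.** The documents give no weight SD, so the following are assumptions: height 1.63 m, an SD derived from the eligible BMI range, a 5 kg true difference between arms, and a correlation ρ of 0.8 or 0.9 between pre-pregnancy and 12-month weight. From the documents: BMI 19 to 40, and 10 women per group (Section 2, Study Population).

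- Weight = BMI × 1.63²: 50.5 kg at BMI 19, 66.4 kg at 25, 106.3 kg at 40. The range is 55.8 kg.
- SD: 55.8/6 = 9.3 kg, or 55.8/√12 = 16.1 kg if evenly spread.
- For scale, the 7% goal at BMI 25 to 40 is 0.07 × 66.4 = 4.6 kg to 0.07 × 106.3 = 7.4 kg.
- SE of a two-arm difference = SD × √(2/10): 4.16 and 7.20 kg.
- Probability of the wrong sign = Φ(−5/SE).
- For ANCOVA, SD is multiplied by √(1−ρ²). For change, with equal SDs at both times, SD is multiplied by √(2(1−ρ)).

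| Analysis | SD 9.3 kg | SD 16.1 kg |
|---|---|---|
| 12-month weight, unadjusted | 0.115 | 0.244 |
| Change, ρ = 0.8 | 0.029 | 0.136 |
| ANCOVA, ρ = 0.8 | 0.023 | 0.124 |
| Change, ρ = 0.9 | 0.004 | 0.060 |
| ANCOVA, ρ = 0.9 | 0.003 | 0.056 |

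Most of the gain comes from using the baseline at all. Moving from change to ANCOVA adds little.

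**4. What the missing analysis could show.** With 5/10 against 2/10 meeting the goal (illustrative counts), the risk difference is 0.30, with Newcombe 95% CI −0.11 to 0.60. At assumed true rates of 20% and 40%, a Fisher exact test with 10 per arm at two-sided 0.05 has power of about 0.06. The result would be descriptive.

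**The case against.** The strongest reply is that keeping weight continuous may be deliberate and sensible. Dichotomising 10 women per arm discards information, and the interval in step 4 shows how little a proportion would settle. Aim 2 is handled the same way: it asks about results in the normal range and is analysed as continuous glucose. Outcome 3 is headed as postpartum weight loss, and Section 4 gives reduced weight retention as one purpose of the later study, so an ANOVA addresses part of the objective. Finally, the weights are collected, so attainment could be tabulated at any time.

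Some of this stands. A continuous analysis is worth keeping, and the proportions cannot be confirmatory. The precision figures apply only if unadjusted 12-month weight is meant, and they rest on assumed SDs and correlations. The 5 kg difference is also an assumption: the 7% goal is a within-woman change that applies only at BMI 25 or above, so it does not establish 5 kg as a difference between arms. ANCOVA is a gain in efficiency and does not correct a bias.

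The mismatch is not removed. Aim 3 as worded asks who meets the goal, and the plan does not say why that was set aside. Leaving the tabulation for later means that the denominator and the continuous measure would be chosen after the data are seen.

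**Conclusion.** The concern holds. On any reading of the Section 4 sentence, attainment of the stated weight goal is not analysed in any arm, so Aim 3 is not answered in the terms in which it is posed. This conclusion needs no assumption beyond the text.

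The second part is conditional. If the ANOVA is on 12-month weight without baseline, a true 5 kg benefit would point the wrong way about 11 to 24% of the time, against about 2 to 12% (ρ = 0.8) or 0.3 to 6% (ρ = 0.9) with adjustment, under the assumptions in step 3. If change was meant, the figures are already about 3 to 14% and 0.4 to 6%, and only the missing goal analysis remains.

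This should be fixed. It affects whether a stated aim is answered and how useful the pilot's estimates are. It does not affect safety or error rates.

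**What to change.** Replace the Aim 3 sentence in Section 4 with two elements.

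1. Report the number and proportion of women meeting the BMI-specific goal in each arm, and risk differences for Groups 2 and 3 against Group 1 with 95% CIs, labelled descriptive because there are 10 women per arm. State the denominator, including how women without a 12-month weight are counted.
2. Name one continuous outcome, either 12-month weight or percent change from pre-pregnancy weight. Analyse it by ANCOVA with pre-pregnancy weight as covariate and contrasts of Groups 2 and 3 against Group 1.

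The cost is a short rewrite of one sentence and one residual degree of freedom (30 − 3 = 27 becomes 26 with all women observed). No new data are needed: Section 9 already lists height, weight immediately before pregnancy and 1-year weight for all three groups among the data sent to the analysts.
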